13.5. Essential Documentation Requirements

The Sponsor or Sponsor's representative will collect from the investigational site the required essential regulatory documents per ICH guidance prior to voxelotor shipment to the site.

13.6. Informed Consent

13.6.1. Participant

Each participant will be provided with oral and written information describing the nature, purpose and duration of the study, participation/termination conditions, and risks and benefits. Prior to initiation of any study-related procedures, participants will sign and date the ICF to participate in the study.

Participants unable to sign the ICF may participate in the study if a legal representative or witness provides the consent (in accordance with the procedures of ICH-GCP and local regulations) and the participant confirms his/her interest in study participation. The participant will be informed that they can freely withdraw consent and stop participation in the study at any time with no prejudice post study care.

13.6.2. Investigator Responsibilities

It is the Investigator's responsibility to obtain written informed consent from the participant after adequate explanation of the objectives, methods, anticipated benefits, and potential risks of the study and before any study procedures are commenced. The participant should be given a copy of the ICF in their native language. The informed consent processes should be recorded in the source documentation. The original copies of the signed and dated informed consent must be retained in the institution's records and are subject to inspection by representatives of the Sponsor, or representatives from regulatory agencies.

13.7. Confidentiality

The Investigator must ensure that the participant's privacy is maintained. On the CRF and other documents submitted to the Sponsor, participants will be identified by a participant study number only. Documents that are not submitted to the Sponsor (eg, signed ICF) should be kept in a strictly confidential file by the Investigator.

The Investigator shall permit authorized representatives of the Sponsor, regulatory agencies, and IECs/IRBs to review the portion of the participant's medical record that is directly related to the study. As part of the required content of informed consent, the participant must be informed that his/her records will be reviewed in this manner.

13.8. Regulatory, Ethical and Legal Obligations

The study will comply with the General Data Protection Regulation (GDPR) 2018, and applicable local data protection regulations. Data collected will be pseudonymized.

The processing of the personal data of participants will be minimized by making use of a unique participant study number only on study documents and electronic database(s).

All study documents will be stored securely and only accessible by study staff and authorized personnel. The study staff will safeguard the privacy of participants' personal data. The participant information sheet/informed consent for the study will inform the participant of their rights and provide appropriate contact details of the Data Protection Officer.

13.9. Study Documentation and Data Storage

The Investigator must retain a comprehensive and centralized filing system of all study-related documentation that is suitable for inspection by the Sponsor and representatives of regulatory authorities.

The Investigator must retain essential documents as detailed in Section 14.2. Participant files and other source data (including copies of protocols, original reports of test results, investigational agent dispensing logs, correspondence, records of informed consent, and other documents pertaining to the conduct of the study) must be kept for the maximum period of time permitted by the institution. Documents should be stored in such a way that they can be accessed/data retrieved at a later date. Consideration should be given to security and environmental risks.

No study document will be destroyed without prior written agreement between the Sponsor and the Investigator. Should the Investigator wish to assign the study records to another party or move them to another location, written agreement must be obtained from the Sponsor.

14. DATA HANDLING AND RECORDKEEPING

14.1. Inspection of Records

GBT will be allowed to conduct site visits to the investigation facilities for the purpose of monitoring any aspect of the study. The Investigator agrees to allow the monitor to inspect the drug storage area, study drug stocks, drug accountability records, participant charts, study source documents, and other records relative to study conduct.

The Investigator agrees to maintain a Regulatory Binder in a current, organized fashion; this Binder will contain documentation supportive of the protocol and GCP compliance of the study. The contents of the Binder will be organized according to the standards of ICH E6, Section 8 (Essential Documents). The Investigator agrees to make this Binder accessible to the monitor, auditor, and representatives of regulatory agencies and the IEC/IRB.

14.2. Retention of Records

The Investigator will maintain adequate records, including participants' medical records, laboratory reports, signed consent forms, drug accountability records, safety reports, information regarding participants who discontinued the protocol, and any other pertinent data. All study records must be retained for at least 2 years after the last approval of a marketing application in the US or an ICH region and until (1) there are no pending or contemplated marketing applications in the US or an ICH region or (2) at least 2 years have elapsed since the formal discontinuation of clinical development of the investigational product under study.

The Investigator/institution should retain participant identifiers for at least 15 years after the completion or discontinuation of the study. Study participant files and other resource data must be kept for the maximum period of time permitted by the hospital/institution but not less than 15 years. These documents should be retained for a longer period, if required by the applicable regulatory requirements or by the Sponsor. GBT must be notified with retention if the Investigator/institution are unable to continue with the maintenance of study participant files for the full 15 years. All study records must be stored in a secure and safe facility.

The Investigators must retain protocols, amendments, IEC/IRB approvals, copies of the Form FDA 1572, signed and dated consent forms, medical records, CRFs, drug accountability records, all correspondence and any other documents pertaining to the conduct of the study.

If the Investigator moves, withdraws from an investigation or retires, the responsibility for maintaining the records may be transferred to another person who will accept responsibility. Notice of transfer must be made to and agreed by the Sponsor. The Investigator must notify the Sponsor immediately in the event of accidental loss or destruction of any protocol records.

14.3. Disclosure of Information

Participants' medical information obtained as a result of this study is considered confidential, and disclosure to third parties, other than those noted in this protocol, is prohibited. Subject to any applicable authorization(s), all reports and communications relating to participants in this study will identify participants only by initials and number. Medical information resulting from a participant's participation in this study may be given to the participant's personal physician, other authorized parties, or to the appropriate medical personnel responsible for the participant's

participation in this clinical study. Data generated in this study will be available for inspection on request by the FDA or other governmental regulatory agency auditors, the Sponsor, the Sponsor's Medical Monitor (or designee), and their designated representatives, the IEC/IRB, and other authorized parties. All information concerning the study medication and the Sponsor's operations (such as patent applications, formulas, manufacturing processes, basic scientific data, or other information supplied by the Sponsor and not previously published) are considered confidential and shall remain the sole property of the Sponsor. The Investigator agrees to use this information only in conducting this study and to not use it for other purposes without the Sponsor's prior written consent. The information developed in this clinical study will be used by the Sponsor in the clinical development of voxelotor and, therefore, may be disclosed by the Sponsor as required, to authorized parties (including its corporate partners for the study drug, if any, and their designated representatives), other clinical Investigators, pharmaceutical companies, the FDA, and other governmental agencies. Any information, inventions, discoveries (whether patentable or not), innovations, suggestions, ideas, and reports made or developed by the Investigator(s) as a result of conducting this study shall be promptly disclosed to the Sponsor and shall be the sole property of the Sponsor. The Investigator agrees, upon the Sponsor's request and at the Sponsor's expense, to execute such documents and to take such other actions as the Sponsor deems necessary or appropriate to obtain patents in the Sponsor's name covering any of the foregoing.

15. PUBLICATION POLICY

The Sponsor intends to publish the results of the study once all participants have completed the study and the study has been analyzed.

The Investigator or the Sponsor may not submit for publication or present the results of this study without allowing each of the other parties to review and comment on the prepublication manuscript, as defined in the site's clinical trial agreement.

The Investigator may not submit any of the results of the study for publication without the prior consent of the Sponsor.

16. FINANCING AND INSURANCE

The Sponsor has subscribed to an insurance policy covering, in its terms and provisions, its legal liability for injuries caused to participating persons and arising out of this research performed strictly in accordance with the scientific protocol as well as with applicable law and professional standards.

Financial Disclosure statements will be handled in a separate agreement apart from the protocol, kept on file and submitted, as applicable, with any subsequent license application.

APPENDIX A. SCHEDULE OF ASSESSMENTS: DOSE ESCALATION PHASE

Visit (days)	Screening	Periods 1, 2, 3, and 4					Period 4 Only
	Day -21 to Day -1	Day 1	Day 2	Day 3	Day 7 ± 1	Day 14 ± 2	
Visit to investigational site	X	X	X		X	X	X
Phone call				X			
Informed consent	X						
Review inclusion/exclusion criteria	X	X					
Medication and medical history	X	X					
Height ^a /weight/BMI	X	X					X
Vital signs ^b	X	X	X			X	
ECG (12-lead) in triplicate ^c	X	X			X		X
Physical examination ^d	X	X					
Serum pregnancy test (females of child-bearing potential only)	X						
Urine pregnancy test (females of child-bearing potential only) ^e		X					
FSH (postmenopausal females only)	X						
Coagulation panel (PT, PTT, INR)	X						
Serology panel (Hepatitis A, B, C, and HIV ^f)	X						
Blood for hematology and chemistry	X	X	X			X	X
Hemoglobin genotype testing (if not already available)	X						
Fetal hemoglobin	X						
Urinalysis	X						
Erythropoietin		X					
RBC deformability, dense cells (if feasible)		X					
Hemoximetry (P50 and P20) ^g		X	X		X		X
Study drug administration ^{h,i}		→					
Blood for PK assessment ^j		X	X		X		X
CGI-C and PGI-C		X ^k					X

Visit (days)	Screening	Periods 1, 2, 3, and 4					Period 4 Only
	Day -21 to Day -1	Day 1	Day 2	Day 3	Day 7 ± 1	Day 14 ± 2	Day 21
Concomitant medications	X	X	X	X	X	X	X
Adverse events	X	X	X	X	X	X	X

BID, twice daily; BMI, body mass index; CGI-C, Clinical Global Impression of Change; ECG, electrocardiogram; FSH, follicle-stimulating hormone; HIV, human immunodeficiency virus; INR, international normalized ratio; P20, partial pressure at which hemoglobin is 20% saturated with oxygen; P50, partial pressure at which hemoglobin is 50% saturated with oxygen; PGI-C, Patient Global Impression of Change; PK, pharmacokinetic; PT, prothrombin time; PTT, partial thromboplastin time; RBC, red blood cell.

Note: For procedures scheduled to be performed at the same timepoint, the order of assessments is as follows: vital signs, PK sample collection, blood draw for PD/safety laboratory assessments, ECGs. If times are delayed due to technical difficulties, this will be noted but not considered a protocol violation. RBC deformability and dense cells will be tested if feasible by the local or collaborating lab at the time of collection.

^a Height to be assessed at Screening only.

^b Vital signs (heart rate, blood pressure, and body temperature [only on Day 1] will be measured after a participant has rested for at least 5 minutes in the seated or supine position. While at the investigational site, vital signs will be obtained in the morning prior to dosing and other planned assessments.

^c Triplicate ECGs should be recorded at screening. On Day 1 of Period 1 only, triplicate ECGs should be recorded at 3 timepoints prior to dosing (-45 min, -30 min, and -15 min); the predose PK sample should be collected immediately prior to the -30-minute ECGs; and postdose triplicate ECGs (after the morning dose) should be recorded within 15 min following the 2-hour PK sample collection. On Day 1 in Periods 2, 3, and 4, on Day 7 in all periods, and on Day 21 in Period 4, predose triplicate ECGs should be recorded within 15 minutes following the predose PK sample collection. Postdose triplicate ECGs (after the morning dose) should be recorded within 15 min following the 2-hour PK sample collection. All triplicate ECGs will be centrally read. Participants should rest supinely for at least 10 min prior to ECGs.

^d A complete physical examination should be performed at the Screening visit; Physical examinations after the Screening visit may be abbreviated. Abbreviated physical examination should include at a minimum: Examination of skin, cardiovascular and respiratory systems, abdominal examination, and symptom-directed examination.

^e If positive urine test, serum pregnancy test will be done to confirm result.

^f A test for HIV will be performed only if clinically indicated.

^g On Day 1, samples for hemoxygometry will be obtained predose (within 30 minutes prior to dosing) and at 8 hours postdose. Samples will only be predose on all other scheduled days. The predose sample will be obtained prior to dosing at the investigational site.

^h Visits should take place in the morning. Participants are instructed to hold study drug until a predose blood sample for PK is obtained at the investigational site.

ⁱ During Period 1 (1500 mg daily), study drug will be administered as 3 × 500 mg tablets once daily. During Periods 2, 3, and 4, study drug will be administered BID (Period 2: 2000 mg daily, 2 × 500 mg BID; Period 3: 2500 mg daily, 3 × 500 mg in morning and 2 × 500 mg in evening); Period 4: 3000 mg daily, 3 × 500 mg BID).

^j On Day 1, blood samples for PK will be obtained predose (within 30 minutes prior to dosing) and at 2 hours (± 15 min) and 8 hours (± 15 min) postdose. On Day 2, blood samples for PK will be obtained predose only, and on Day 7, will be obtained predose and 2 hours postdose. The predose sample will be obtained prior to morning dosing at the investigational site.

^k Periods 2, 3, and 4 only (equivalent to Day 21 for Periods 1, 2, and 3, respectively).

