APPENDIX B. SCHEDULE OF ASSESSMENTS: OBSERVATION PERIOD AND SAFETY FOLLOW-UP

Visit (weeks)	Observation Period							Safety Follow-up ^a
	Week 1		Week 3	Week 6	Week 12	Week 18	Week 24/ EOT	
Visit (days)	Day 1 ^b	Day 7	Day 21	Day 42	Day 84	Day 126	Day 168	Day 196
Visit to investigational site	X	X	X	X	X	X	X	X
Weight/BMI							X	X
Vital signs ^c		X	X	X	X	X	X	X
ECG (12-lead) in triplicate ^d					X		X	X
Physical examination ^e							X	X
Urine pregnancy test (females of child-bearing potential only) ^f		X			X		X	
Blood for hematology and chemistry		X	X	X	X	X	X	X
Urinalysis							X	
Erythropoietin							X	
RBC deformability, dense cells (if feasible)					X		X	
Hemoximetry (P50 and P20) ^g		X	X		X		X	
Study drug administration ^{h,i}	→							
Blood for PK assessment ^j		X	X		X		X	
CGI-C and PGI-C					X		X	
Concomitant medications		X	X	X	X	X	X	X
Adverse events		X	X	X	X	X	X	X

BMI = body mass index; CGI-C, Clinical Global Impression of Change; ECG, electrocardiogram; EOS, End of Study; EOT, End of Treatment; P20, partial pressure at which hemoglobin is 20% saturated with oxygen; P50, partial pressure at which hemoglobin is 50% saturated with oxygen; PGI-C, Patient Global Impression of Change; PK, pharmacokinetic; RBC, red blood cell.

Note: For procedures scheduled to be performed at the same timepoint, the order of assessments is as follows: vital signs, PK sample collection, blood draw for PD/safety laboratory assessments, ECGs. If times are delayed due to technical difficulties, this will be noted but not considered a protocol violation. RBC deformability and dense cells will be tested if feasible by the local or collaborating lab at the time of collection.

^a Safety Follow-up visit will take place 28 days post final dose.

^b Day 1 of the observation period is the same as the last day of the dose escalation period. If the participant begins the observation period after a dose reduction, a Day 1 clinical visit is needed, which would collect the same assessments as the Day 21 visit in the Dose Escalation Period (Appendix A).

^c Vital signs (heart rate and blood pressure) will be obtained in the morning prior to dosing and other planned assessments.

^d Single safety ECG at Week 12, Week 24/ET, and Week 196 (EOS).

^e Physical examinations may be abbreviated. Abbreviated physical examination should include at a minimum: Examination of skin, cardiovascular and respiratory systems, abdominal examination, and symptom-directed examination.

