^f If positive urine test, serum pregnancy test will be done to confirm result.

^g Samples for hemoximetry will be obtained predose (within 30 minutes prior to dosing) at the investigational site.

^h Visits should take place in the morning. Participants are instructed to hold study drug until a predose blood sample for PK is obtained at the investigational site.

ⁱ During the observation period, the participant will receive their maximum tolerated dose or 3000 mg daily.

^j During the observation period, blood samples for PK will be obtained predose (within 30 minutes prior to dosing) at the investigational site.

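### Eight-hour P50/P20 and % Hb occupancy are sampled only on Day 1 of each period, so they are never observed under 3000 mg/day and the 1500 mg value is a first-dose value

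*Combined protocol and SAP*

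**What the plan says.** Section 10.1.3 lists P50 and P20, and % Hb occupancy, each at 8 and 24 hours after dosing. It names no visit and no dose level. Section 10.4 presents data by maximum dose level and describes no P50/P20 or occupancy summary. Section 1.5.1 plans to compare three weeks of 1500 mg with the highest tolerated dose at steady state.

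The sampling times are in the footnotes to the schedules:

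- **Hemoximetry, escalation (Appendix A, footnote g):** "On Day 1, samples for hemoxygometry will be obtained predose (within 30 minutes prior to dosing) and at 8 hours postdose". For the rest, "Samples will only be predose on all other scheduled days".
- **PK, escalation (Appendix A, footnote j):** Day 1 is predose, 2 h and 8 h. Then "On Day 2, blood samples for PK will be obtained predose only, and on Day 7, will be obtained predose and 2 hours postdose". Period 4 Day 21 is marked for PK, but the footnote gives no times. The ECG instructions in Section 8.18 and footnote c imply predose and 2 h.
- **Observation period (Appendix B, footnotes g and j):** "Samples for hemoximetry will be obtained predose (within 30 minutes prior to dosing) at the investigational site"; PK is predose as well.
- **Entry to observation after a dose reduction (Appendix B, footnote b):** "a Day 1 clinical visit is needed, which would collect the same assessments as the Day 21 visit in the Dose Escalation Period". Hemoximetry at that visit is predose only.
- **Regimens (Appendix A, footnote i):** "Period 3: 2500 mg daily, 3 × 500 mg in morning and 2 × 500 mg in evening" and "Period 4: 3000 mg daily, 3 × 500 mg BID". Only the evening dose differs between these two periods.

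**The concern.** An 8-hour sample on the first day of a period mostly reflects the doses taken before that day. For Period 4 it reflects nothing else, because the morning dose is the same as in Period 3 and the larger evening dose has not yet been taken. A value filed under Period 4 would then be a 2500 mg/day value.

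The Period 1 value has the opposite problem. It follows a single dose with no accumulation, so it does not describe 1500 mg/day after three weeks. The Period 2 and Period 3 values carry over from the level before. The only level with an 8-hour sample at its own steady state is 2500 mg/day, and that sample is collected under the Period 4 label.

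The trial exists to describe doses above 1500 mg and to set them against 1500 mg. An 8-hour contrast of Period 4 with Period 1 would compare an accumulated 2500 mg/day value with a first-dose value, and would overstate the steady-state rise in drug amount. Since Section 10.4 does not say how these samples are assigned to a dose level, nothing in the plan prevents that reading.

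**Working it through.** **1. Daily doses (Appendix A, footnote i).** 3 × 500 = 1500; 2 × 500 × 2 = 2000; 3 × 500 + 2 × 500 = 2500; 3 × 500 × 2 = 3000 mg. All four agree with Section 3.2.

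**2. Dose taken in the 24 h before each Day 1 8-hour sample.**

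| Period | Nominal mg/day | Doses in the preceding 24 h | Total mg |
|---|---|---|---|
| 1 | 1500 | first dose, 1500 | 1500 |
| 2 | 2000 | morning 1000 | 1000 |
| 3 | 2500 | evening 1000 + morning 1500 | 2500 |
| 4 | 3000 | evening 1000 + morning 1500 | 2500 |

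The totals are the same for periods of 18, 21 or 24 days and for an evening dose 8.5 to 14 h after the morning dose. No listed 8-hour sample follows a dose specific to 3000 mg/day.

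**3. Occupancy scale.** Section 1.5.1 gives mean occupancy of 29% at 1500 mg and a projected 49.3% at 3000 mg. Neither figure is specific to 8 hours. Linear interpolation in daily dose (an assumption) gives, at 2500 mg, 29 + (49.3 − 29) × 1000/1500 = 42.5%. The shortfall is 49.3 − 42.5 = 6.8 points, and the ratio is 42.5/49.3 = 0.86.

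**4. Drug amount (illustration).** The model is linear one-compartment with bolus doses, the evening dose at 12 h and 21 days per level. The documents give no half-life, so 12 to 72 h is assumed, with k = ln 2/half-life. At 8 h:

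- Steady state, morning dose A and evening dose B: (A·e^(−8k) + B·e^(−20k)) / (1 − e^(−24k)).
- Period 1 Day 1 over its own steady state: 1 − e^(−24k).
- Period 4 Day 1 over 3000 mg/day steady state, once 2500 mg/day has settled: (1500 + 1000·e^(−12k)) / (1500 + 1500·e^(−12k)).
- Period 4 over Period 1, both at steady state: 1 + e^(−12k).
- Period 4 Day 1 over Period 1 Day 1: (1500 + 1000·e^(−12k)) / (1500·(1 − e^(−24k))).

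For a 12 h half-life, e^(−12k) = 0.5 and e^(−24k) = 0.25. These give 0.75, 2000/2250 = 0.89, 1.50 and 2000/1125 = 1.78. Dose-by-dose superposition gives:

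| Half-life (h) | 12 | 24 | 36 | 48 | 72 |
|---|---|---|---|---|---|
| Period 1 Day 1 / own steady state | 0.75 | 0.50 | 0.37 | 0.29 | 0.21 |
| Period 4 Day 1 / 2500 mg/day steady state | 1.00 | 1.00 | 1.00 | 1.00 | 0.999 |
| Period 4 Day 1 / 3000 mg/day steady state | 0.89 | 0.86 | 0.85 | 0.85 | 0.84 |
| Period 4 / Period 1, as scheduled | 1.78 | 2.94 | 4.13 | 5.33 | 7.72 |
| Period 4 / Period 1, steady state | 1.50 | 1.71 | 1.79 | 1.84 | 1.89 |
| Period 4 / Period 1, both on Day 7 | 1.50 | 1.72 | 1.85 | 1.98 | 2.27 |
| Period 4 Day 21 / Period 1 Day 1 | 2.00 | 3.41 | 4.85 | 6.28 | 9.15 |

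Period 2 Day 1 is 0.73 to 0.75 of its own steady state and Period 3 Day 1 is 0.83 to 0.94. Not every contrast is inflated: with a 12 h half-life, Period 2 over Period 1 is 1.00 both as scheduled and at steady state. With first-order absorption of 0.5/h, an evening dose at 10 h, or both, the scheduled Period 4 to Period 1 range is 1.7 to 7.9 and the steady-state range 1.45 to 1.89.

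**The case against.** The strongest reply is that no listed endpoint goes unmeasured. Section 10.1.3 does not ask for steady state, and every period supplies an 8-hour value on Day 1 and a 24-hour value at Day 2 predose. The Period 4 to Period 1 contrast at 8 hours is not a planned analysis. The steady-state comparison in Section 1.5.1 can be made from predose samples: Day 1 predose of Periods 2 to 4 is the end-of-period trough of the level before (for CGI-C and PGI-C, footnote k treats that visit as "equivalent to Day 21 for Periods 1, 2, and 3, respectively"), and predose hemoximetry and PK and the Day 7 2-hour PK cover 3000 mg/day. Population PK can use Day 1 samples with the actual dose history. The size in drug amount rests on an assumed sixfold range of half-life and is not on the P50/P20 or occupancy scale.

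All of that stands as a limit on importance. It does not supply an observed 8-hour P50/P20 or occupancy value at 3000 mg/day, since a model prediction is not the listed measurement. It also leaves open how a Day 1 sample would be labelled. The result in step 2 needs no half-life.

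**Conclusion.** The concern holds. As scheduled, the 8-hour P50/P20 and occupancy endpoints are not observed under 3000 mg/day, and the 1500 mg value is a first-dose value. This rests on one assumption, that the evening dose is taken after the 8-hour draw; the documents give no clock time. Confidence in the schedule reading is high. The sizes are less certain: 6.8 points depends on linear interpolation, and the drug-amount ratios depend on the assumed half-life and on linear kinetics.

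Primary and secondary endpoints are untouched. The point is worth considering because the remedy is cheap; it does not threaten the trial's main conclusions.

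**What to change.** - **Appendix A, footnotes g and j:** move the 8-hour hemoximetry and PK draws from Day 1 to the existing Day 7 visit of every period (hemoximetry predose and 8 h; PK predose, 2 h and 8 h). Keep the Period 1 Day 1 8-hour draw only if a first-dose profile is wanted. State the Period 4 Day 21 PK times.
- **Section 10.1.3:** name the visit for the 8-hour and 24-hour values. The Day 7 predose sample, taken 24 h after the Day 6 morning dose, can be the 24-hour partner.
- **Section 10.4:** label any retained Day 1 8-hour value by the dosing before it (Period 1 as first dose, Period 4 Day 1 as 2500 mg/day). Report time since last dose for the 24-hour value: 24 h under once-daily dosing, about 12 h after the evening dose under twice-daily dosing.
- If an 8-hour draw is added on Period 4 Day 21, use it only as an observed value at 3000 mg/day. Set against Period 1 Day 1 it would give 2.0 to 9.2, worse than the present schedule.

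The cost is a sampling amendment with no new visits, no added draws and no dosing change. Day 7 becomes about 6 hours longer and Day 1 about 6 hours shorter. The first-day 8-hour value after each increase is lost, with its Day 2 pairing, and anyone who leaves a level before Day 7 contributes no 8-hour value there.

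Day 7 is not a complete cure if the half-life is long. At 72 h, Period 1 Day 7 is 0.80 of steady state (0.75 on Day 6, the early edge of the window), and the Day 7 ratio of 2.27 is still about 20% above 1.89 (2.27/1.89 = 1.20). If the schedule cannot change, the minimum is the labelling text, or restating the endpoint as predose or model-predicted.
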